1. PROJECT TITLE

Developing a Text Message Enhanced Physical Activity Intervention for Latino Men (Activo)

4. ESTIMATED DURATION OF THE STUDY

2 Years

5. LAY LANGUAGE SUMMARY OR SYNOPSIS (no more than one paragraph)

The aim of this study is to build upon our tailored print intervention by developing new text-delivered intervention materials to complement our print-based physical activity (PA) intervention. In Phase 1 we will conduct 6 focus groups with Mexican and Mexican American (MA) men to determine content, frequency, and types of text messages desired, and to identify cultural themes to incorporate into existing and new materials. Themes from the focus groups and sample text messages will be presented to a confirmatory focus group panel. Phase 2 will be a 6-month pilot randomized controlled trial with MA men (N=60) to test the text-enhanced, Spanish language, individually tailored PA intervention vs. publicly available, Spanish language health education materials, including information on PA, diet, and stress management. This will be followed by post-intervention qualitative interviews to solicit suggestions for improvements to help further refine the program. The proposed pilot will support a future R01 to establish the efficacy of this multi-media, multi-level PA intervention for MA men.

6. SPECIFIC AIMS

Primary Aims:

1. Aim 1: To conduct the formative research necessary to develop new text message-based materials based on Social Cognitive Theory (SCT) constructs and a resulting text messaging intervention program to complement and enhance our current print-based PA intervention for MA men.

2. Aim 2: To determine the feasibility, acceptability, and preliminary efficacy of the text message enhanced PA intervention for MA men. We hypothesize that those randomized to the text message enhanced PA intervention condition will report greater increases in weekly minutes of PA after six months than those randomized to the health education control condition.

7. BACKGROUND AND SIGNIFICANCE

Back and Significance

The proposed research addresses serious public health concerns (inactivity, health disparities) in a large, rapidly growing population of Mexican and Mexican American (MA) men who are markedly less physically active than men of other ethnicities and suffer from higher prevalence of conditions related to sedentary lifestyle. While this population is clearly in need of physical activity (PA) interventions, to date none have specifically targeted MA men. In fact, the majority of PA interventions for Latinos have exclusively included women and/or are designed around female preferences. The proposed study will address the needs and barriers to PA in MA men by developing text message-delivered intervention materials based on Social Cognitive Theory (SCT) to complement an individually tailored, theory-based print material PA intervention for Spanish speaking MA men. Text messaging could be a particularly effective and appealing channel for increasing PA in this target population as it allows for participant interaction, real-time accountability, and immediate feedback, features which MA men in the demonstration trial of our print intervention specifically requested. Text-based interventions have been shown to improve a number of health behaviors, including PA. A recent review of texting interventions found that they were generally well received and effective in reducing inactivity, weight, and waist circumference, and a meta-analysis found a moderate effect size ($g = 0.54$) for using mobile devices to increase PA. However, few of these trials targeted underserved populations, and none specifically targeted Latinos. Cell phone ownership is high in Latino adults (86% vs. 84% in non-Latino

Whites), and Latinos are actually the most likely to use mobile phones for text messaging, with 85% reporting regularly sending and receiving texts (compared to 79% of Whites). Thus this is a familiar, convenient channel for delivering new intervention materials. Additionally, as Latinos also face environmental barriers to PA, in the current proposal we will enhance the individually tailored psychosocial print-based materials by developing materials targeting barriers in home and work environments. This multi-media, multi-level approach has potential for broad reach at relatively low cost, which could help reduce health disparities.

Preliminary Studies/Previous Work

Study Team: [name] (PI) and colleagues have spent the past 25 years developing and testing empirically supported individually tailored PA interventions (e.g., R01HL64342, R01HL69866). This intervention was culturally and linguistically adapted for Latina women and successfully implemented in this underserved population in two studies (R21NR009864, R01NR011295). We have extensive experience in designing, implementing and evaluating theory-based, culturally-adapted PA interventions for Latinos (Drs. [name], [name], [name], [name], [name]), using text messaging for promoting behavior change ([name]), environmental influences on PA ([name]), recruitment and retention of Latinos (Drs. [name], [name], [name], [name], [name]), and statistics ([name]). See Table 1.

Table 1. Past Studies of Research Team that Directly Relate to the Current Proposal

PI/ Funding: Description	Results
Culturally and linguistically adapting an empirically supported theory-based print PA intervention for Latinas	
[name] (PI) R21NR009864: 1) 25 cognitive interviews to clarify content of translated/ back translated materials and measures; 2) 6 focus groups on PA barriers for Spanish speaking Latinas (N=34); 3) Pilot RCT of adapted intervention (N = 93 Latinas).	Themes from participant feedback were incorporated into the intervention including: 1) Literacy level; 2) Daily stressors/Negative Mood; 3) Lack of Time; 4) Neighborhood Safety; 5) Lack of Motivation; 6) Partner Support. RCT findings: Mean increase of 130.71 min/week ($sd=242.52$) from baseline to six months amongst intervention participants compared to 84.92 min/week ($sd=118.26$) amongst controls.
[name] (PI) R01NR011295: Ongoing RCT to test the efficacy of the culturally/ linguistically adapted, individually tailored print intervention for Latinas (N=268).	82% speak only Spanish or more Spanish than English at home. Six month findings indicate significantly greater increases in at least moderate intensity PA from baseline to 6 months ($M=71.66$ min/week, $sd=89.92$) for Intervention vs. Control ($M=29.58$ min/week, $sd=84.37$), $p<.01$.
Preliminary efforts to identify and address the specific PA intervention needs and preferences of MA men	
[name] (PI) UCSD Intramural funds: Individual interviews with Spanish speaking MA men (N=10) about PA intervention needs and preferences.	Culturally-specific themes included 1) Importance of family, 2) Gender roles (“Machismo”), 3) Demanding and irregular work schedules, 4) Preference for team sports, 5) Cultural norms, 6) Preference for Spanish language, and 7) A need for accountability. ¹⁵ Intervention was adapted in response to feedback. See Appendix H for full details of cultural modifications.
[name] (PI) UCSD Intramural funds: Single arm demonstration trial of the resulting, tailored theory-based print PA intervention for Spanish-speaking MA men (N=10) followed by individual interviews.	100% retention and significant increase in PA at 3 months (mean increase =124.20 min/week, $sd=154.86$, $p=0.032$). Participants indicated high satisfaction but that participation and motivation could be enhanced by: 1) greater accountability, 2) more contact with staff, 3) shorter and more frequent tips, and 4) real-time updates on PA opportunities. Participants also expressed interest in receiving PA text messages.
Text Message Intervention Studies	
[name] (PI) R21CA115615: Focus groups to identify quantity/timing of text messages for weight loss intervention in overweight/ obese men & women. RCT to test resulting text message intervention (N=65).	At 4 months, intervention group lost more weight than controls (4.34 pounds more; $p=0.02$). Adherence to responding to text messages was high. Overall satisfaction with the intervention was also high, with 96% of participants stating that they would recommend the intervention to friends and family.
[name] (PI) R01CA138730: Ongoing follow-up to R21 using formative research to develop Spanish-language intervention and then conduct a 12-month RCT (N=298).	Focus group feedback was used to develop culturally appropriate text messages for Latinos. Overweight/obese English (n=236) and Spanish (n=62) speakers were randomized to a 3 arm weight loss intervention: text message only, text message plus counseling, or usual care.

8. PROGRESS REPORT

N/A

9. RESEARCH DESIGN AND METHODS

Overall Design: The present study will be conducted in two phases. In **Phase 1** we will conduct formative research to further enhance our empirically supported, theory-based, personally tailored PA print materials by 1) developing interactive and tailored text message PA intervention components to meet the needs and preferences of Spanish-speaking MA men, and 2) incorporating culturally specific themes and creating materials tailored to neighborhood environments. In **Phase 2**, we will conduct a pilot RCT to test the text-enhanced individually tailored PA intervention for MA men vs. a health education control arm.

Phase 1: Formative Research: Our goal with the formative research phase of this study is to inform the development of a text message enhancement to address the concerns of MA men identified in our pilot work, and to incorporate culturally specific themes into text and print intervention materials. Specifically, we plan to build upon our existing theory-based individually tailored intervention by developing interactive and tailored text message intervention materials that address the feedback of the MA men by increasing accountability, providing more frequent contacts, allowing for interactivity between participants, and improving motivation. Focus groups will also be used to determine the most useful features of tailored environmental reports.

[figure not shown]
We will conduct 6 focus groups with 6 to 8 MA men per group or one-on-one meetings with a staff member if needed. Eligibility includes: a) self-identified as MA; b) able to speak and read Spanish; c) currently engaging in less than 60 minutes of activity per week; and d) no health-related contraindications for becoming more active including history of coronary heart disease, diabetes, stroke, osteoarthritis, or orthopedic problems (see Phase 2 for further detail). The focus groups will be lead by a bilingual, bicultural researcher; each focus group is expected to last 1 hour.

We will use data from the focus groups to develop the text messaging intervention materials and program and identify cultural themes to incorporate into print and text materials. After the text message enhancement has been developed we will invite a random sub-sample of the men who participated in the focus group to attend a confirmatory panel (n=6). This provides an opportunity to confirm intervention preferences and correct any misunderstandings, as well as allow the participants to further elaborate upon initial focus group responses. Sample text messages will be provided so participants can approve/disapprove any changes and new content.

Qualitative Data Analysis: For qualitative data analysis, all focus groups will be audio taped and translated into English. A content analysis will be conducted to generate themes related to PA intervention needs and preferences of the MA men that will aid in refining the text message enhancement. Bicultural staff members and other investigators, will analyze the transcripts in a two-step process. In the first step, two investigators will read through the transcripts to look for themes that are consistent with prior literature and theory (a deductive process) and gender- and cultural-specific themes that are revealed by the participants themselves to be common across MA men (an inductive process) to develop a set of codes/labels and definitions for the themes. In the second step, two investigators will use this set of codes to label each statement within the transcripts. Transcript coding will be compared between investigators and inconsistencies will be discussed among all investigators until consensus agreement of the appropriate code is achieved. All text and coding will be done with the use of NVivo qualitative software. This content analysis will be used to inform the development of the text-enhanced PA intervention for MA men.

Phase 2: Pilot Randomized Controlled Trial: We will randomize 60 MA men into a 6-month pilot trial of the resulting text-enhanced PA intervention for MA men vs. a health education control. The procedures for recruitment, pre-trial screening, and monitoring derive from our team's experiences conducting similar trials (e.g., R21NR009864, R01NR011295, R01HL64342). See Figure 1. Although it is preferred that participants attend all visits in person, they will be informed during the telephone screening process that modified versions of study visit can be offered via phone in the event that they are not able to travel to the study site.

Figure 1: Phase 2 Randomized Controlled Trial Intervention Schema

Telephone Screening: To reduce the likelihood of adverse events, participants will be phone screened for factors that may increase risk of injury. Potential participants with medical or psychological problems that could make adherence with the study protocol difficult or dangerous will not be included. Exclusions include history of coronary heart disease, history of myocardial infarction, symptoms of angina, type 1 diabetes, uncontrolled hypertension, stroke, osteoarthritis, osteoporosis, orthopedic problems that would limit activity during the following six months, currently engaging in more than 90 minutes of activity per week or any other serious medical condition that would make physical activity unsafe. Other exclusion criteria will include hospitalization due to a psychiatric disorder in the past 3 years, BMI above 45 kg/m² and/or taking medication that may impair physical activity tolerance or performance (e.g., beta blockers). After screening is completed, eligible and interested participants must agree to be randomly assigned to one of the intervention conditions and provide written consent to participate in the research protocol. In addition, participants will be informed that in the event that they cannot attend an in-person visit at any of our study sites, they will have the option to complete the visit via phone. All in-person visits (including those occurring at our off-site UCSD facilities) will be conducted by our trained study staff. Descriptions of both in-person visits and phone visits are provided below.

In-Person Visits:

Orientation/Measurement Visit: Following telephone screening for eligibility, interested individuals will be asked to attend an in-person orientation session in which a bilingual/bicultural research staff member will provide information about the study. During this session, all questions regarding participation in the study will be answered. Participants will then be asked to read and sign a consent form approved by the university's institutional review board. Participants will also complete anthropometric measures and an initial battery of psychosocial measures during this visit. Self-reported height and weight will be accepted. At the end of this visit, the participant will be given and instructed on how to use an accelerometer during the next seven days.

Baseline/Randomization Visit: One week after the orientations/measurement visit, the participant will return the accelerometer, complete a 10-minute treadmill walk at moderate intensity (3-4 miles per hour) to demonstrate understanding of moderate intensity activity, and complete the 7-Day Physical Activity Recall (PAR). At that time, participants will be randomly assigned to one of two conditions: 1) a text-message enhanced, Spanish language, individually tailored, print-based physical activity intervention; or 2) a Spanish language print-based health education control.

Months 1-6: After randomization, participants will fill out monthly mailed questionnaires for 6 months. Individuals randomized to the physical activity arm will receive individually tailored reports generated by a computer expert system along with messages appropriate for their stage of motivational readiness for physical activity adoption immediately following completion of the questionnaires. Those randomized to the health education control condition will also receive monthly mailed questionnaires and materials on health

topics related to cardiovascular disease, such as nutrition, physical activity, and stress management information. Participants will also be receiving text messages related to exercise or health and wellness depending on their group assignment. The schedule and amount of contact will be the same across conditions.

6 Month Assessment: All participants will be asked to attend an in-person visit at 6 months to recomplete all measures completed during the initial measurement visit and baseline visit.

Telephone Visit:

In the event that participants cannot attend any of our in-person visits, they will have the option to complete the visit via telephone. Details of each of these visits are provided below.

Orientation/Measurement Visit:

Following telephone screening for eligibility, participants will be asked to schedule a phone call visit in which a bilingual/bicultural research staff member will provide information about the study and review the consent documents. Details of the informed consent process via phone are addressed in section 12. Also following the telephone screening, participants will be mailed the UCSD IRB approved informed consent documents along with a battery of psychosocial questionnaires. Once the participants have received the mailings, a phone call with a bilingual/bicultural research staff member will occur where the participants will be provided with information about the study and the staff will review the informed consent documents.

If the participant decides to participate in the program, they will then be asked to sign the consent documents and mail back in a pre-paid envelope that we will provide. Once we have received the signed informed consent documents, a staff member will inform the participants that they can now complete the mailed questionnaires and return them to us. The informed consent documents and questionnaires will be sent in separate envelopes when being mailed, although they will be sent at the same time-point. It will be clearly stated on the questionnaire packet that they are NOT to complete the battery of questionnaires until we have received their signed informed consent document in the mail.

Once we have received the signed informed consent documents and completed psychosocial measures, staff will then schedule another call with the participant to provide additional information regarding the randomization visit as well as instructions on how to use an accelerometer that will be mailed to them. During this phone visit, the following components cannot be conducted: STOHFLA measure and anthropometric measures including height, weight, blood pressure, and bioelectrical impedance analysis. Self-reported height and weight will be collected as an alternative.

Baseline/Randomization Visit: Project staff will mail the accelerometer as well as the materials for the randomization visit. Upon receiving the accelerometer, participants will be asked to wear this device for 7 days and return to us in a provided pre-paid envelope. Once our staff has received this device, they will schedule the phone randomization visit. During the randomization visit participants will complete the 7-Day Physical Activity Recall (PAR) and be randomly assigned to one of two conditions: 1) a text-message enhanced, Spanish language, individually tailored, print-based physical activity intervention; or 2) a Spanish language print-based health education control. During this phone visit the 10-minute treadmill walk cannot be conducted.

6 Month Assessment: Similar to the baseline/randomization visit, in the event that participants cannot attend their in-person visit, they will have the option to complete the visit via phone. During this phone visit, the following components cannot be conducted: the 10-minute treadmill walk and anthropometric measures (as stated above). Self-reported height and weight will again be collected as an alternative.

Treatment Conditions

Text-Enhanced Physical Activity Intervention Arm: The Spanish-language PA intervention is based on SCT and Transtheoretical Model (TTM), and emphasizes behavioral strategies for increasing activity levels (i.e., goal-setting, self-monitoring, problem-solving barriers, increasing social support, rewarding oneself for

meeting PA goals). At baseline participants will receive a pedometer, set a detailed PA goal, problem-solve around barriers to achieving their PA goal, and receive recommendations for walking/jogging routes, parks with athletic equipment and playgrounds, and other places to be active surrounding their work or home. They will receive regular mailings: weekly in month 1, bi-weekly in months 2 and 3, and monthly in months 4 to 6. Mailings consist of: 1) Manual matched to the participant's current level of motivational readiness to change, based on TTM; 2) Individually tailored computerized expert system feedback reports based on the participant's answers to monthly questionnaires (see Measures) that compares participants to their prior responses (progress feedback) and to individuals who are physically active (normative feedback) on: self-efficacy for PA and cognitive and behavioral strategies associated with PA behavior change (processes of change); 3) PA tip sheets addressing PA barriers. These print materials have been modified for MA men based on cultural themes identified during our formative work and trial (e.g. focus on family, team sports, "Machismo," etc.). Participants will also receive the text message intervention that will be developed as part of Phase 1 of this proposal. Based on our previous formative research, reviews of the literature, and theories of behavior change we anticipate using interactive, tailored, and culturally adapted text messages to: 1) increase accountability, 2) help navigate their environment, 3) increase competition, 4) increase motivation, 5) inform about local events, 6) focus on the family, 7) provide social support, and 8) increase the study's connectivity with participants. See Table 3 for proposed text messages, examples of text messages, and how they fit with SCT. Participants will receive \$5 per month to defray the costs of the text messages.

Table 3: Types of text messages to be used based on Qualitative Research and Social Cognitive Theory		
Social Cognitive Theory Construct	Intervention needs/Type of SMS	Types of text messages
Behavioral Capability/ Reinforcement	Need for Accountability/ Interactive, sent at specified times/days	1) Matched to day/time of exercise goal: "Have you exercised yet today? YES/NO"; "YES"; "Great job!" 2) Text message to log/collect info
Reciprocal determinism	Built environment/ Tailored information	1) Places to be active near their home/work: "There's a great park with a soccer field at 1234 Main St."
Observational Learning	Increase Competition/ Group messages	1) Highlight success and encourage competition: "Someone reported over 12,000 steps yesterday, can you beat him?"
Outcome expectations/ Self-efficacy	Increase motivation through culturally relevant benefits and barriers/ Informational	1) Benefits of PA: "Having a rough day? Exercising is a great way to lower stress!" 2) Address barriers: "Work day seem too busy to be active? Look for places that you could get 10 min in, like during a lunch break"
Reciprocal determinism	Local activities/ Group messages	1) Text messages about community events: "Fiesta del Sol is this weekend, it's a great place to go walking with the family."
Observational Learning/ Self-efficacy	Focus on family/ Activity prompts	1) Text messages targeting the family: "Is the family home? Go on a walk together before dinner time!"
Observational Learning/ Outcome expectations	Social Support/ Participant Interactive	1) Way for participants to communicate with each other through group text messages via the server.

Health Education Control arm: The health education control arm will receive the publicly available NHBLI Spanish-language booklets on heart-healthy behaviors for Latinos, which include information on PA, diet, and stress management. Similar to intervention participants, control participants will receive tip sheets on related health topics. The health education content was vetted in our individual interviews with MA men who expressed a strong interest in receiving and reading these materials. Mailed contacts for the control group will be on the same schedule as the mailed contacts for the intervention condition (weekly month 1, bi-weekly months 2 and 3, and monthly months 4 to 6). Participants in the health education control arm will also complete monthly questionnaires relevant to the topics of their materials.

List of Measures

7-Day PAR Interview provides an estimate of total weekly minutes of PA.

Demographics measure will assess age, education, income, race, and marital status, and acculturation scale.

Stages of Change for Physical Activity (SCPA) measure has successfully been used to stage-match treatment.

Processes of Change for Physical Activity (POC) measure contains 10 subscales that address a variety of

cognitive/behavioral processes related to PA behavior change.

Self-Efficacy For Physical Activity (SE) measures self-efficacy to become physically active across diverse contexts.

Neighborhood Environment Walkability Scale, Abbreviated (NEWS-A) assesses various aspects of the built environment related to walking, neighborhood aesthetics, and traffic.

ActiGraph. For the week prior to each 7-Day PAR assessment, all participants will wear an Actigraph, which measures movement and intensity of activity.

Health-O-meter medical scale will be used to measure body weight and height.

Short Test of Functional Health Literacy in Adults (STOFHLA) tests literacy for English and Spanish speaking patients in healthcare settings.

Consumer Satisfaction Measure was used by our research team in past trials and adapted for the current study to assess feasibility/acceptability of this the text-enhanced PA intervention.

Wellness Questionnaire assesses knowledge about health topics presented in the control materials.

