16. PRIVACY AND CONFIDENTIALITY CONSIDERATIONS INCLUDING DATA ACCESS AND MANAGEMENT

Informed Consent: There is a potential risk of participating in a group orientation session. During the consenting process other participants will be in the room, which could lead to a loss of your confidentiality. While we ask all participants to protect and respect other people's confidentiality, we cannot guarantee that all participants will abide by this request. Although information about the study and the informed consent process will be conducted in a group setting, the research staff will also be available to discuss any questions or concerns privately. Participants will also have the option of reading, discussing and signing the consent forms in a private area if they prefer. In addition, we will take all necessary and possible precautions to avoid loss of confidentiality during group orientation sessions, including only referring to individuals by their first names, with no mention of last names.

Procedure for Collection of Data: Research participants will complete baseline questionnaires, as dictated by the study protocol. All data collected are considered part of the subject's confidential record and will be placed in a locked file cabinet within 24 hours of acquisition as designated by the study's Data Manager. All data will remain confidential. A file that associates the subject name with that subject's study identification number will be maintained. This file will remain locked in a file cabinet and will not be stored with the actual study data.

Accelerometers: The data collected from the accelerometers will be used as primary data. Data downloaded from the accelerometers will be incorporated into the database that contains all other collected study data. Backup copies of the original downloaded files will be maintained on the university network.

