The primary aim of our pilot trial is to determine the feasibility and acceptability of the text-enhanced PA intervention. We will consider the intervention feasible if at least 80% of participants are retained at the 6-month follow-up. The intervention will be considered acceptable if at least 80% of participants respond favorably ("satisfied" or "very satisfied") to the question "In general how satisfied were you with the intervention?". Although interest is in the feasibility and acceptability of the text-enhanced PA intervention arm, we will calculate these rates for both groups and compare them using chi-squared tests. In addition, our data analytical strategy is designed to examine whether there are treatment effects favoring the text-enhanced PA intervention while assuring control for potential confounds not adequately controlled for by the randomization. Thus as a preliminary step, we will assess potential between-group differences in baseline characteristics (demographics, baseline activity level) using graphical methods, non-parametric and parametric tests as appropriate (e.g., Wilcoxon rank-sum test for skewed data, t-tests for normally distributed continuous data & chi-squared tests for categorical data). Any variables not balanced by randomization will be controlled for as covariates in subsequent analyses. We will estimate the preliminary efficacy of intervention compared to control using a generalized linear model in which we regress minutes/week of moderate to vigorous PA (*as measured by accelerometers*) at 6 months on treatment assigned, baseline value of the outcome and potential confounders (including those variables not balanced by randomization). To avoid the effects of outliers, we will apply a normalizing transformation (if necessary) to the outcome prior to analysis. Modeling is done using a likelihood-based approach and thus makes use of all available data (intent-to-treat sample) to produce consistent estimates of the regression parameters. We are aware that effect size estimates with small samples have large standard errors and wide confidence intervals. To determine the sample size for a clinical trial, the trial needs to have adequate power to detect a clinically relevant difference between treatment

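### Neither randomisation pathway checks that the baseline accelerometer file is usable before allocation, so men can enter without the baseline value that the efficacy model needs

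*Combined protocol and SAP*

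**What the plan says.** In section 9, the in-person Baseline/Randomization Visit begins with the device: "One week after the orientations/measurement visit, the participant will return the accelerometer". The treadmill walk and the 7-Day PAR follow, and then "At that time, participants will be randomly assigned to one of two conditions". In the telephone version of the visit the device comes back by post first: "Once our staff has received this device, they will schedule the phone randomization visit". The condition there is receipt of the device, not the content of its file.

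Section 16 gives these data high status: "The data collected from the accelerometers will be used as primary data". The data analysis paragraph at the end of the document estimates efficacy with a "generalized linear model in which we regress minutes/week of moderate to vigorous PA", measured by accelerometer, "at 6 months on treatment assigned, baseline value of the outcome and potential confounders". On missing data it says "Modeling is done using a likelihood-based approach and thus makes use of all available data (intent-to-treat sample").

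Other places bear on the point:
- The eligibility and exclusion criteria (sections 9 and 10) do not require usable wear.
- Section 14 makes the baseline treadmill walk a condition of eligibility. Nothing similar is stated for the accelerometer.
- Section 20 pays $10 for returning the device, not for having worn it.
- The research assistant's role description, just before section 22, lists downloading and cleaning device data as a skill, with no timing relative to randomisation.

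**The concern.** A returned accelerometer may have been worn too little, not worn at all, or have failed. If that is discovered only after allocation, the baseline cannot be measured again. Under the Text-Enhanced Physical Activity Intervention Arm in section 9, a man receives a pedometer, sets an activity goal and works through barriers at baseline, so any later wear in that arm is already exposed to treatment.

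The efficacy model needs a baseline value for each man. A likelihood method copes with a missing 6-month outcome, but a regression that conditions on baseline has no contribution from a man whose baseline is missing, unless that value is imputed or modelled jointly with the outcome. The plan states neither. Followed as written, it could remove randomised men from an analysis that it describes as intent-to-treat, and reduce the precision of an estimate from a trial of only 60.

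**Working it through.** The plan states no figure on this point, and the available text gives no alpha, power or standard deviation for N = 60, so there is nothing to reproduce. The sizes below are illustrative.

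**Inputs from the documents**
- Men randomised: 60 (section 9).
- Retention: 80%, the feasibility threshold in the data analysis paragraph, so 60 × 0.80 = 48 men at 6 months.

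**Assumptions**
- Share of baseline wears that are unusable: q = 5% to 20%.
- Correlation between baseline and 6-month activity: r = 0.5.
- Usable baseline and retention are independent.

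**Step 1: men without a baseline, 60 × q**
- 60 × 0.05 = 3.
- 60 × 0.20 = 12.

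This applies q to both pathways, since neither has a check. The documents give no split between in-person and phone visits. If 30 men came in person, that pathway alone would account for 30 × 0.05 = 1.5 to 30 × 0.20 = 6.

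**Step 2: chance that at least one man is affected, 1 − (1 − q)^n**
- At q = 5% and n = 60: 1 − 0.95^60 = 0.954.
- At q = 5% and n = 30: 1 − 0.95^30 = 0.785.

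**Step 3: men are dropped**
- Complete cases, 48 × (1 − q): 48 × 0.95 = 45.6 and 48 × 0.80 = 38.4, so about 46 to 38 men instead of 48.
- Standard error ratio, 1/√(1 − q): 1/√0.95 = 1.026 and 1/√0.80 = 1.118, a rise of about 3% to 12%.

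**Step 4: men are kept with an imputed baseline**

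On a scale where the outcome variance is 1, a man with a measured baseline has residual variance 1 − r² = 0.75. A man with a common imputed value has residual variance 1. The average is 0.75 + 0.25q, so the standard error ratio is √(1 + q/3).
- q = 5%: √1.0167 = 1.008.
- q = 20%: √1.0667 = 1.033.

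The rise is about 1% to 3%. The men stay in the analysis, and only the gain from covariate adjustment is lost for them.

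**The case against.** The strongest reply is that the protocol is silent on a check rather than opposed to one. At the in-person visit the device comes back before a 10-minute walk and an interview, and staff are said to know how to download it. A procedures manual could hold the step. The available analysis text also breaks off mid-sentence. This stands as a limit on wording: the documents show that men can be randomised without a baseline, not that they will be.

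A reader might infer that same-visit randomisation of in-person men is the defect. The documents do not support that, since the phone pathway has time for a check but also conditions only on receipt.

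A reader might also infer that the treatment comparison is biased. Baseline wear precedes allocation, so its failure is unrelated to arm, and dropping those men does not by itself favour either side.

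Nor is a loss of 3% to 12% in precision unavoidable. It follows only if men are dropped, and a pre-specified method for missing baselines would remove most of it. If men with failed wear are also the ones who drop out, the loss is smaller again.

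A further objection is that requiring valid wear for entry would act as a compliance run-in. In a pilot judged on 80% retention, that could flatter the result. This is right, and it shapes the remedy. What remains is that imputation keeps the man but cannot restore the measurement, while a check before allocation often can.

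**Conclusion.** The point holds for both pathways, limited to the available text. Nothing between return of the device and allocation secures the baseline value on which the efficacy model conditions, and no rule covers its absence. What is at stake is the precision of the preliminary efficacy estimate and the claim to analyse everyone randomised. Retention and satisfaction, which decide feasibility and acceptability, do not use baseline accelerometry.

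The size is small to moderate and rests wholly on an assumed failure rate, with the correlation and independence assumptions also outside the documents. The plan already concedes that small-sample effect estimates are imprecise. This is a worthwhile, inexpensive improvement and not a flaw that threatens the trial.

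**What to change.** In both pathways:
1. Define a minimum-wear rule for a usable accelerometer week; the available text has none.
2. Download the device and check it against that rule before the allocation is opened. By phone, do this on receipt, before the call is scheduled.
3. If the file fails, offer one repeat 7-day wear. The measures list in section 9 ties device wear to the week before each 7-Day PAR, so take the PAR after the repeat week, or repeat it if already done.
4. Randomise afterwards whether or not the second wear is usable, so that the check does not become a compliance filter.
5. State in the analysis plan that any man still without a baseline stays in the analysis, through baseline imputation or a joint likelihood model for baseline and 6-month values.

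The check takes a few minutes with skills that staff are already said to have. Because it comes before allocation, it does not disturb assessor blinding. The downside is about one extra week and one extra visit or call for each man whose first wear fails, and a few might lose interest while they wait.
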